**Table 5-4 Factors and covariates for the main analysis for secondary estimand**

Factors and covariates at baseline	Type	Categories
Randomised treatment	Categorical fixed effect	IDeg, IDet
Region	Categorical fixed effect	Europe (Austria, Denmark, Greece, Ireland, Italy, United Kingdom and Serbia), North America (Canada), South America (Argentina and Brazil) and Asia/Oceania (Australia, Israel and Russia).

Statistical Analysis Plan  
 Trial ID: NN1250-4300  
 UTN: U1111-1191-3018  
 EudraCT No: 2017-000048-17

**CONFIDENTIAL**

Date: 27 January 2021  
 Version: 2.0  
 Status: Final  
 Page: 22 of 34

**Novo Nordisk**

Stratification factor	Categorical fixed effect	Randomised as pregnant and planned continuous use of CGM, randomised as pregnant and no planned continuous use of CGM, randomised as non-pregnant and planned continuous use of CGM, randomised as non-pregnant and no planned continuous use of CGM
Pregnancy status at randomisation and treatment baseline HbA 1c	Interaction factor	Treatment baseline for HbA 1c for randomised pregnant , Treatment baseline for HbA 1c for randomised non-pregnant

\*Baseline refers to treatment baseline

### 5.3.3 Sensitivity analysis

To investigate the sensitivity of the primary analysis results, complementary and separate analyses will be performed for the primary and secondary estimand in line with guidelines from EMA47 and the U.S. National Research Council. The evaluation of the robustness of the primary analysis results will be based on approaches using multiple imputations. Similar sensitivity analyses are made for the primary and secondary estimand:

1. A multiple imputation analysis based on the PPpregnant : The analysis is similar to the primary analysis for the primary and secondary estimand, but based on PPpregnant. The analysis investigates the impact of protocol deviations on the primary analysis.
2. A multiple imputation tipping point analysis based on the FASpregnant : In this sensitivity analysis, missing data will first be imputed according to the primary analysis for the primary and secondary estimand. Second, for the IDeg arm a penalty will be added to the imputed values of last planned HbA1c prior to delivery after GW 16. The approach is to gradually increase this penalty by 0.5 until the confirmed HbA1c conclusion from the primary analysis is reversed. The analysis investigates how sensitive the results of the primary analyses for the primary/secondary estimands are towards the assumption that missing data have the same mean level as available data within the groups specified for the imputation.

Statistical Analysis Plan  
 Trial ID: NN1250-4300  
 UTN: U1111-1191-3018  
 EudraCT No: 2017-000048-17

**CONFIDENTIAL**

Date: 27 January 2021  
 Version: 2.0  
 Status: Final  
 Page: 23 of 34

**Novo Nordisk**

**Table 5-5 Statistical analysis to address primary and secondary objectives**

SI No	Endpoints	Landmark visit	Endpoint type	Imputation approach and Statistical model	Analysis set	Sensitivity analyses
Primary Endpoint						
1	Last planned HbA 1c prior to delivery after GW 16	Last planned visit prior to delivery after GW 16	Continuous	MI ANCOVA	FAS pregnant	
 
MI based on the PPpregnant
 
MI tipping point analysis based on the FASpregnant
 

Secondary Endpoint						
1	HbA 1c ≤ 6.0% (42 mmol/mol) from last planned HbA 1c prior to delivery after GW 16 (yes/no)	Last planned visit prior to delivery after GW 16	Categorical	MI Logistic regression	FAS pregnant	NA
2	HbA 1c ≤ 6.5% (48 mmol/mol) from last planned HbA 1c prior to delivery after GW 16 (yes/no)	Last planned visit prior to delivery after GW 16	Categorical	MI Logistic regression	FAS pregnant	NA
3	Last planned average PPG prior to delivery after GW 16	Last planned visit prior to delivery after GW 16	Continuous	MI ANCOVA	FAS pregnant	NA
4	Last planned FPG prior to delivery after GW 16	Last planned visit prior to delivery after GW 16	Continuous	MI ANCOVA	FAS pregnant	NA

Statistical Analysis Plan  
Trial ID: NN1250-4300  
UTN: U1111-1191-3018  
EudraCT No: 2017-000048-17

~~CONFIDENTIAL~~

Date: 27 January 2021  
Version: 2.0  
Status: Final  
Page: 24 of 34

**Novo Nordisk**

## 5.4 Secondary endpoints analysis

### 5.4.1 Efficacy endpoints

#### 5.4.1.1 Supportive secondary endpoints

The supportive secondary endpoints will be evaluated for:

- The primary estimand based on  $FAS_{\text{pregnant}}$  using the in-trial data
- The secondary estimand based on  $FAS_{\text{pregnant}}$  using the on-treatment data

No sensitivity analyses are planned for these.

#### Supportive maternal binary efficacy endpoints

- $HbA_{1c} \leq 6.0\%$  (42 mmol/mol) from last planned  $HbA_{1c}$  prior to delivery after GW 16 (yes/no)
- $HbA_{1c} \leq 6.5\%$  (48 mmol/mol) from last planned  $HbA_{1c}$  prior to delivery after GW 16 (yes/no)

For both estimands missing data for the responses of the above binary endpoints will be obtained from dichotomizing imputed values of  $HbA_{1c}$ . Hence, 1000 imputed datasets simulated as for the primary analyses of the primary and secondary estimand for  $HbA_{1c}$ , respectively, will be applied in the corresponding analyses of the dichotomized endpoints. The imputed complete data sets will be analysed using a logistic regression model with treatment, stratification factor and region as categorical fixed effects and a pregnancy status at randomisation-by-baseline  $HbA_{1c}$  interaction. Inference comparing treatments will be drawn using Rubin's rule. The odds ratio between IDeg and IDet will be estimated together with the corresponding two-sided 95% CI. The p-value corresponding to a two-sided test of no difference (odds ratio equal to 1) will be reported.

#### Supportive maternal continuous efficacy endpoints

- Last planned average PPG prior to delivery after GW 16
  - Average of three main meals
- Last planned FPG prior to delivery after GW 16

Average PPG is defined as the average of the available BG measurements 90 minutes after breakfast, lunch and main evening meal respectively. If all 3 measurements are missing the average PPG is missing. Subjects with missing average PPG at baseline are excluded from the PPG analysis and subjects with missing FPG at baseline are excluded from the FPG analysis. The above continuous endpoints will be analysed using similar modelling approaches as for the primary endpoint with the associated baseline response as a covariate.

Statistical Analysis Plan  
 Trial ID: NN1250-4300  
 UTN: U1111-1191-3018  
 EudraCT No: 2017-000048-17

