## 17.4 Secondary endpoints

### 17.4.1 Efficacy endpoints

#### Supportive secondary endpoints

The supportive secondary endpoints will be evaluated for:

- The primary estimand based on FASpregnant using the in-trial data
- The secondary estimand based on FASpregnant using the on-treatment data

No sensitivity analyses are planned for these.

Data from the in-trial pregnancy and post-pregnancy periods will be summarised and plotted by treatment arm and visit based on FASpregnant. Data from the on-treatment period will be presented

Protocol  
 Trial ID: NN1250-4300  
 UTN: U1111-1191-3018  
 EudraCT no.: 2017-000048-17

CONFIDENTIAL

Date: 17 December 2020  
 Version: 4.0  
 Status: Final  
 Page: 90 of 110

Novo Nordisk

similarly. In addition, summaries and plots will be presented separately for subjects randomised as pregnant and subjects randomised as non-pregnant.

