**Table 4–2 Overview of defined analysis sets**

Defined Analysis Set	Description
Full analysis set for pregnant women (FASpregnant)	Includes all randomised women who are pregnant during the trial. Subjects in the FAS pregnant will contribute to the evaluation “as randomised”.
Per protocol analysis set for pregnant women (PPpregnant)	Includes subjects from FAS pregnant who: 
 
• Have not violated any inclusion criteria
 
• Have not fulfilled any exclusion criteria
 
• Are exposed to trial drug at least the first four weeks after randomisation or, in case of termination of pregnancy within the first four weeks after randomisation, until time of termination of pregnancy.
 
 Subjects in the PP pregnant analysis set will contribute to the analysis according to the treatment received prior to potential discontinuation of randomised treatment. This will be referred to as contributing to the evaluation “as treated”.
Safety analysis set for pregnant women (SASpregnant)	Includes all randomised women exposed to at least one dose of trial product and who are pregnant during the trial. Subjects in the SAS pregnant will contribute to the evaluation “as treated”.

The primary endpoint and secondary efficacy endpoints are analysed using full analysis set for all pregnant women.

Statistical Analysis Plan  
 Trial ID: NN1250-4300  
 UTN: U1111-1191-3018  
 EudraCT No: 2017-000048-17

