**Novo Nordisk**

## 5 Statistical analyses

### 5.1 General considerations

Results from a statistical analysis will at a minimum be presented by the estimated treatment contrasts for the comparison between IDeg and IDet with associated two-sided 95% confidence intervals (CI) and p-values corresponding to two-sided tests of no difference.

Non-inferiority will be considered confirmed if the upper bound of the CI is strictly below 0.4%. The p-value corresponding to a two-sided test of no difference will also be reported.

The full analysis set for all pregnant women (**FASpregnant**) who contribute to the analysis will be used in the analysis of efficacy endpoints. For further details of how the subjects will be determined whether they contribute to the statistical analysis or not refer to [6.3.1.1](#). For the safety endpoints, the safety analysis set for all pregnant women (**SASpregnant**) will be used. The definition of analysis sets are given in section [4](#).

The treatment baseline value will be used in the statistical models and is defined as the latest available measurement at or before randomisation. For all subjects the treatment baseline value hence corresponds to the value obtained at the randomisation visit (visit 2) if available, or at the screening visit (visit 1). If neither of these measurements have been obtained the treatment baseline will be left missing. For subjects randomised pregnant the pregnancy baseline is derived from the treatment baseline, and the two baseline values will be identical, corresponding to the values obtained at visit 2 or visit 1.

When summarising change from baseline for effect and safety variables assessed during or after the pregnancy period, both treatment baseline and pregnancy baseline variables will be applied. First the treatment baseline described above to illustrate changes since initiation of treatment, second the pregnancy baseline to illustrate changes since early pregnancy.

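### Women with an observed PPG or FPG outcome are dropped if the baseline is missing, so these supportive analyses cover fewer women than the stated full analysis set

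*SAP*

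**What the plan says.** SAP 5.4.1.1 defines average PPG as the mean of whichever 90-minute post-meal readings are available. It adds: "If all 3 measurements are missing the average PPG is missing". The exclusion for PPG comes next: "Subjects with missing average PPG at baseline are excluded from the PPG analysis". A parallel clause covers the other endpoint: "subjects with missing FPG at baseline are excluded from the FPG analysis". Apart from that, both endpoints are modelled like the primary endpoint, with their own baseline as covariate. Table 5-5 lists both as multiple-imputation ANCOVA on FAS_pregnant, with no sensitivity analysis.

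On the analysis set, the sentence under SAP Table 4–2 reads: "The primary endpoint and secondary efficacy endpoints are analysed using full analysis set for all pregnant women". The set is defined as: "Includes all randomised women who are pregnant during the trial". SAP 5.1 narrows this to women who contribute to the analysis: "For further details of how the subjects will be determined whether they contribute to the statistical analysis or not refer to" Section 6.3.1.1. That section decides the matter on delivery and visit timing and does not mention baseline availability.

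On a missing treatment baseline in general, SAP 5.1 says: "If neither of these measurements have been obtained the treatment baseline will be left missing".

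Protocol 17.4.1 says "The supportive secondary endpoints will be evaluated for" the primary and secondary estimands, each on FAS_pregnant. It gives the PPG and FPG model without an exclusion rule. Protocol 17.2 asks that exclusions be sparing, expects none from FAS_pregnant as a rule, and requires any to be documented before database lock.

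**The concern.** The rule treats the two kinds of missing data the wrong way round. If the outcome is missing and the baseline is present, the woman stays and her outcome is imputed. If the outcome was measured and the baseline is missing, she goes. Real outcome data are discarded for lack of a covariate whose only job is to sharpen the estimate.

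Three things follow. Precision is lost. The PPG, FPG and HbA1c results may describe slightly different groups of women. A reader of Table 5-5 would take the denominator to be FAS_pregnant less the women excluded under 6.3.1.1, and it may be smaller. Because no sensitivity analysis is planned for these endpoints, nothing in the planned output would show the effect.

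The usual fallback does not help here. SAP 5.1 lets a screening value stand in for a missing randomisation value. That works for HbA1c, which is measured at screening and needed for eligibility. The flowcharts in Protocol 2.1 and 2.3 schedule FPG and the 9-point profile at visit 2 but not at visit 1, so there is no earlier value to use.

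**Working it through.** **Plan's own figure.** The only sample size in the documents is for HbA1c (Protocol 17.1). A non-central t calculation (one-sided 2.5%, 80% power, margin 0.4, SD 0.85) gives 144 evaluable women. Then 144/0.9 = 160, and 160/0.9 = 177.8, rounded up to 178. This matches the protocol, but no power is stated for PPG or FPG, so it does not bear on the point.

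**Inputs.** FAS_pregnant has 188 women (SAP 6.3.1.1). The planned share delivering before gestational week 16 is 10% (Protocol 17.1), and those women do not enter the analysis. Contributing women: 188 × 0.9 = 169.2, about 169. The share m with missing baseline is not given and is assumed.

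**Formulas.** Women lost: k = 169 × m, rounded. Standard error (SE) under exclusion relative to complete baselines for all: √(169/(169 − k)). The fair comparison is with imputation. If the baseline–outcome correlation is ρ, a woman with an observed baseline contributes information in proportion to 1/(1 − ρ²), and a woman with a filled baseline contributes 1. The SE under exclusion relative to imputation is then

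√{[(169 − k)/(1 − ρ²) + k] / [(169 − k)/(1 − ρ²)]}.

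Example, m = 10%, ρ = 0.5: 152/0.75 = 202.7; (202.7 + 17)/202.7 = 1.084; the square root is 1.041.

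**Simulation.** 4000 runs with 169 women, 1:1 allocation, no treatment effect, one standardised baseline covariate, and baseline more often missing when its value is high. Exclusion was compared with a mean-filled baseline plus a missing indicator.

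| Assumed missing | Lost / left | SE vs complete baselines | SE vs imputation, formula (ρ = 0.3 / 0.5) | SE vs imputation, simulation (ρ = 0.3 / 0.5) |
|---|---|---|---|---|
| 5% | 8 / 161 | +2.5% | +2.2% / +1.8% | +2.1% / +2.1% |
| 10% | 17 / 152 | +5.4% | +5.0% / +4.1% | +4.3% / +3.0% |
| 20% | 34 / 135 | +11.9% | +10.9% / +9.0% | +11.4% / +9.2% |

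At 1% missing, 2 women are lost and the SE rises by 0.6% against complete baselines.

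**Bias.** The true difference was zero. The largest average estimate in any scenario was 0.0048 SD under exclusion and 0.0036 SD under imputation. The Monte Carlo standard error for the former is 0.1516/√4000 = 0.0024, so neither method shows material bias.

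**Text check.** The protocol's list of supportive endpoints, its PPG/FPG model and SAP Table 5-5 carry no baseline condition. SAP Appendix 2 lists changes to pre-eclampsia rates, the birth-weight unit, the infant adverse-event window and the added category for unavailable outcomes. The baseline exclusion is not among them.

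**The case against.** The strongest reply is that the SAP only spells out what the protocol implied. The protocol puts the baseline response in the model and leaves a missing treatment baseline missing, so an ANCOVA would lose these women anyway. Protocol 17.2 does not forbid exclusions; it asks that they be documented before database lock, and the SAP does write this one down. Complete-baseline ANCOVA is also common and was specified in advance. This stands in large part. A reader might infer a flat contradiction of the full analysis set, and the documents do not support that. They do support a narrower statement: the set named for these endpoints and the set that will be analysed differ, and neither Table 5-5 nor Appendix 2 says so.

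A reader might also infer that one incomplete diary or one non-fasting visit removes a woman. Neither is right. Average PPG is missing only when all three post-meal readings are absent, so a single reading keeps her in. Protocol 8.2 requires fasting attendance at randomisation, and Protocol 8.5.2 provides for a non-fasting FPG sample to be re-scheduled or re-drawn. FPG is lost only if no valid baseline sample results. Both rules suggest that the missing share may be small.

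Finally, comparing exclusion with complete baselines overstates what can be gained, because imputation does not recover everything. The columns against imputation are the ones to use.

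**Conclusion.** The point holds as a minor one. Women with a measured PPG or FPG outcome are dropped when the baseline is missing, the analysed set is then smaller than the one stated, and Appendix 2 does not record it. Only the two continuous supportive endpoints are touched.

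Two stronger readings are not supported. The primary HbA1c result is not at risk, because the exclusion sentence does not apply to it and it has a screening value to fall back on. Nor is there evidence of a biased treatment contrast: the baseline is due at or before randomisation, so treatment cannot influence whether it is missing, and the simulation showed no material bias.

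The size is unknown. For an assumed 5%, 10% or 20% missing, about 8, 17 or 34 of 169 women would be lost, and the SE would be about 2%, 3–4% or 9–11% above that under imputation. These figures rest on the planning value of 10% for early delivery, an assumed baseline–outcome correlation of 0.3 to 0.5, and a simulation with a single covariate and no missing outcomes. If only one or two baselines are missing, the effect is negligible.

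**What to change.** Keep every FAS_pregnant woman who qualifies under SAP 6.3.1.1, and delete the two exclusions from 5.4.1.1. In their place:

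1. Before any outcome imputation, fill a missing baseline PPG or FPG with the mean pooled over arms within pregnancy status at randomisation, using neither treatment nor outcome. Visit 55 values should not be used, since they come after randomisation.
2. Add a missing-baseline indicator to the models.
3. Run the planned multiple imputation and ANCOVA as they stand.
4. Report the complete-baseline analysis as a sensitivity analysis, with the number of women affected per arm.

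Step 1 has to be separate. The primary-estimand imputation in SAP 5.3.2.1 runs within groups defined by arm and treatment discontinuation, so a baseline filled inside it would depend on arm and on post-randomisation events.

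The cost is one extra programming step and one or two extra model terms. In the small discontinued groups the indicator may not be estimable, and the plan's existing fall-back to simpler models would then need to cover it.

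If the exclusion is kept, the least that is needed is to list it in Appendix 2, state the reduced set in Table 5-5, and report the numbers excluded per arm.

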**CONFIDENTIAL**

Date: 27 January 2021  
 Version: 2.0  
 Status: Final  
 Page: 25 of 34

**Novo Nordisk**

## 5.4.2 Safety endpoints

### 5.4.2.1 Maternal safety endpoints

#### Maternal safety endpoints assessed during and after the pregnancy period

Summaries will be based on SASpregnant unless otherwise specified.

**Table 5-6 Analysis of supportive maternal safety endpoint**

Endpoint	Endpoint type	Analysis method	Analysis set	Further information
Number of hypoglycaemic episodes by classification	Discrete	Summary by treatment arm separately for randomised pregnant and randomised non-pregnant *	SAS pregnant	Refer to protocol section 17.4.2.1  For completeness we have also presented a summary based on full analysis set (in-trial data)
Development of sight-threatening retinopathy from treatment baseline as well as from pregnancy baseline to the end of treatment visit	Categorical	Summary by treatment arm separately for randomised pregnant and randomised non-pregnant (Shift table)	SAS pregnant	Refer to protocol section 17.4.2.2
Pre-eclampsia	Discrete	Summary by treatment arm separately for randomised pregnant and randomised non-pregnant *	SAS pregnant	Refer to protocol section 17.4.2.2
Mode of delivery	Discrete	Summary by treatment arm separately for randomised pregnant and randomised non-pregnant	SAS pregnant	Refer to protocol section 17.4.2.2
Change in body weight from pregnancy baseline to last	Continuous	Summary by treatment arm and visits separately for randomised pregnant	SAS pregnant	Refer to protocol section 17.4.2.2

Statistical Analysis Plan  
 Trial ID: NN1250-4300  
 UTN: U1111-1191-3018  
 EudraCT No: 2017-000048-17

**CONFIDENTIAL**

Date: 27 January 2021  
 Version: 2.0  
 Status: Final  
 Page: 26 of 34

**Novo Nordisk**

planned visit before delivery		and randomised non-pregnant		For completeness we have also presented a summary of change from treatment baseline for randomised non-pregnant subjects.
Number of adverse events during pregnancy period.	Discrete	Summary by treatment arm*	SAS pregnant	

\*The number of subjects with at least one event (N), the percentage of subjects with at least one event (%), the number of events (E) and the event rate per 100 years of exposure (R) will be presented.

Endpoint	Analysis method	Analysis set	Further information
Number of adverse events during pregnancy period.	Summary by treatment arm*	SAS pregnant	
 
• Summaries of TEAEs and of serious TEAEs will be presented as an overview including all TEAEs, serious TEAEs, TEAEs by severity, TEAEs by relation to treatment and TEAEs leading to treatment discontinuation or withdrawal.
 
• Summary tables based on system organ class and preferred terms are made for:               
 
• All TEAEs
 
• Serious TEAEs
 
• TEAEs possibly or probably related to trial product
 
• Severe, moderate and mild TEAEs
 
• TEAEs with preferred term that are experienced by at least 5% of
 
 
 

Statistical Analysis Plan  
 Trial ID: NN1250-4300  
 UTN: U1111-1191-3018  
 EudraCT No: 2017-000048-17

**CONFIDENTIAL**

Date: 27 January 2021  
 Version: 2.0  
 Status: Final  
 Page: 27 of 34

**Novo Nordisk**

			
the subjects in any treatment or by at least 5% of all subjects
 
 
• Summary tables of all SAEs including non-treatment emergent SAEs will be presented including summary tables based on system organ class and preferred terms.
 

--	--	--	---

For further reference on adverse events endpoint related analysis refer to [protocol section 17.4.2.2](#)

### 5.4.3 Pregnancy outcome endpoints

As the following pregnancy outcome endpoints have to be summarised for all infants or foetuses, these will be summarised for the full analysis set for all pregnant women.

#### Supportive continuous and binary pregnancy outcome endpoints :

- Birth weight (g)
- Birth weight SD-score
- Live born infants with birth weight < 10th percentile for gestational age and sex (local references) (yes/no)
- Live born infants with birth weight > 90th percentile for gestational age and sex (local references) (yes/no)
- Pre-term delivery (delivery < 37 completed GWs) (yes/no)
- Early foetal death (delivery < 20 completed GWs) (yes/no)
- Perinatal mortality (death of foetus/infant between  $\geq 20$  completed GWs before delivery and < 1 completed week after delivery) (yes/no)
- Neonatal mortality (death of infant between  $\geq 7$  completed days after delivery and < 28 completed days after delivery) (yes/no)
- Presence of major abnormalities (classified according to EUROCAT) (yes/no) : This endpoint refers to the categorisation determined by the adjudication committee.
- Neonatal hypoglycaemic episodes defined as plasma glucose  $\leq 1.7$  mmol/L (31 mg/dL) during the first 24 hours after birth or  $\leq 2.5$  mmol/L (45 mg/dL) between 24 hours and 48 hours after birth (yes/no)

Statistical Analysis Plan  
Trial ID: NN1250-4300  
UTN: U1111-1191-3018  
EudraCT No: 2017-000048-17

~~CONFIDENTIAL~~

Date: 27 January 2021  
Version: 2.0  
Status: Final  
Page: 28 of 34

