**Novo Nordisk**

## Glossary

Congenital anomaly	A morphological, functional and/or biochemical developmental disturbance in the embryo or foetus whether detected at birth or not. The term congenital anomaly is broad and includes congenital abnormalities, foetopathies, genetic diseases with early onset, developmental delay, etc.
Date of conception	Formation of a viable zygote by the union of the male sperm and female ovum; fertilization. Typically occurs about 11-21 days after the first day of the last period.
Delivery	The visit in which the end of the pregnancy takes place, including live birth, foetal death or termination of pregnancy.
Early foetal death	The death of a foetus < 20 completed gestational weeks.
Ectopic pregnancy	Extrauterine pregnancy, early foetal death, most often in the fallopian tube.
Foetus	Unborn offspring from the embryo stage (> 8 completed gestational weeks) until delivery.
HELLP syndrome	Obstetric complication usually considered a variant or complication of pre-eclampsia (abbreviation for: H aemolysis, E levated L iver enzymes, L ow P latelet count).
Infant	Infant from delivery until the end of the first year of life.
Macrosomia	Birth weight above a defined limit at any gestational age.
Major abnormalities	A life threatening structural anomaly or one likely to cause significant impairment of health or functional capacity and which needs medical or surgical treatment.
Minor anomalies	Relatively frequent structural anomaly not likely to cause any medical or cosmetic problems.
Neonatal mortality	Death of an infant between 7 days and 28 completed days after delivery.
Perinatal mortality	Death of a foetus/infant between $\geq 20$ completed gestational weeks and < 7 completed days after delivery.
Planned caesarean section	A caesarean section which has been planned > 8 hours prior to delivery.
Postpartum	The period beginning immediately after delivery and extending for about six weeks.
Pregnancy outcome	The outcome of the pregnancy which includes three main categories: foetal death, termination of pregnancy, and live birth.
Pre-term delivery	Delivery < 37 completed gestational weeks.
Termination of pregnancy (induced/elective abortion)	Artificial interruption of pregnancy.
Unplanned caesarean section	A caesarean section which has not been planned or planned $\leq 8$ hours prior to delivery.

Protocol  
 Trial ID: NN1250-4300  
 UTN: U1111-1191-3018  
 EudraCT no.: 2017-000048-17

CONFIDENTIAL

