### Reporting of foetal or neonatal death

Foetal or neonatal death as a result of induced abortion should not be reported as an AE, except in situations where the foetus/neonate was deceased prior to the induced abortion.

In case of foetal or neonatal death the following applies:

- In case of foetal or neonatal death e.g. due to spontaneous abortion, ectopic pregnancy or stillbirth, an SAE must be reported with the mother as the subject of the AE.
- In case the foetus/neonate also has a diagnosis e.g. an anomaly, an additional SAE must be reported with the foetus/neonate as the subject of the AE.

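### Early foetal death is timed by delivery in the endpoint but by death in the glossary, which leaves a gap beside perinatal mortality and leaves induced terminations unclassified

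*SAP*

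**What the plan says.** The endpoint appears four times in the same words, in Protocol 4.4 and 17.4.2.3 and in SAP 1.1.2.2 and 5.4.3: "Early foetal death (delivery < 20 completed GWs) (yes/no". The bracket gives gestational age at delivery as the criterion.

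The Protocol Glossary uses a different anchor. Early foetal death is "The death of a foetus < 20 completed gestational weeks". Delivery is "The visit in which the end of the pregnancy takes place, including live birth, foetal death or termination of pregnancy". Termination of pregnancy (induced or elective abortion) is "Artificial interruption of pregnancy", and pregnancy outcome has "three main categories: foetal death, termination of pregnancy, and live birth", so foetal death and termination are kept apart. Ectopic pregnancy is classed as an early foetal death.

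The neighbouring endpoints are timed by death. In SAP 5.4.3 the perinatal entry opens "Perinatal mortality (death of foetus/infant between" and starts at 20 completed weeks. The neonatal entry opens "Neonatal mortality (death of infant between" and covers infants from day 7 after delivery.

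On induced abortion the protocol speaks in several voices:
- The opening paragraph of 12.5.2 counts both spontaneous and induced abortion as kinds of foetal death when it lists the SAEs to report.
- Later in 12.5.2: "Foetal or neonatal death as a result of induced abortion should not be reported as an AE", except where the foetus had already died. The paragraph on induced abortions calls abortion a procedure whose causes are always SAEs.
- 8.4.2 names induced abortion and early foetal death as separate items to record.

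The SAP does not define delivery, does not repeat the glossary, and does not say how terminations are classified. SAP Appendix 2, which lists changes to the planned analyses, does not touch this endpoint.

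**The concern.** Two adjacent mortality endpoints should meet without a gap. Here one is bounded by the date of delivery and the next by the date of death. A foetus that dies shortly before week 20 and is delivered after it can slip between them.

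The second problem is what may enter the endpoint. If the bracket is taken with the glossary meaning of delivery, an induced termination before week 20 meets it. If the glossary meaning of foetal death is applied, it does not. Two programmers working from the same documents could produce different tables.

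Pregnancy outcome is one of the two secondary objectives, and early foetal losses are few. Adding or dropping a handful of cases in one arm can change how the comparison looks.

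**Working it through.** The plan attaches no hypothesis, power or event count to this endpoint, so there is no stated figure to reproduce. The check is to apply the written rules to constructed cases.

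Rules used:
- Bracket alone: delivery before 20 completed weeks (SAP 5.4.3), with delivery as in the glossary.
- Name and bracket together: a foetal death, and delivery before 20 completed weeks.
- Perinatal mortality: death at or after 20 completed weeks and before one week after delivery (SAP 5.4.3).
- Glossary: death of the foetus before 20 completed weeks, termination a separate outcome.

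| Case | Week of death | Week of delivery | Early foetal death, bracket alone | Early foetal death, name and bracket | Perinatal mortality | Early foetal death, glossary |
|---|---|---|---|---|---|---|
| Spontaneous loss | 12 | 12 | yes | yes | no | yes |
| Death in utero, delivered later | 19 | 20 | no | no | no | yes |
| Induced termination of a living foetus | 12 | 12 | yes | unclear | no | no |
| Stillbirth | 25 | 25 | no | no | yes | no |
| Induced termination of a living foetus | 21 | 21 | no | no | unclear | no |

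The second row is the gap. It appears under either reading of the endpoint, because both require delivery before week 20 while perinatal mortality requires death at or after week 20. Neonatal mortality does not catch the case either, since it covers infants only.

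The third and fifth rows turn on whether a termination counts as a foetal death. The glossary and 8.4.2 separate the two; the opening paragraph of 12.5.2 joins them.

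Weight of one case. SAP 6.3.1.1 gives 188 women in the full analysis set for pregnant women, the set that SAP 5.4.3 uses for these endpoints. The split by arm is not given. Randomisation is 1:1, so assume 188 / 2 = 94 per arm, with one pregnancy outcome per woman. Then:
- one reclassified pregnancy: 1 / 94 = 1.06, about 1.1 percentage points;
- two: 2 / 94 = 2.1 points;
- three: 3 / 94 = 3.2 points.

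A split of 90 and 98 would change the single-case figure only to 1 / 90 = 1.11 or 1 / 98 = 1.02 points.

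**The case against.** The strongest reply is that the endpoint's name is itself a glossary term. Read naturally, it requires a foetal death, and the bracket only supplies the timing. Taking the bracket as the whole test would admit a live birth before week 20 as well, since delivery in the glossary includes live birth. With the glossary and 8.4.2 both separating termination from foetal death, a reader who infers that elective terminations are definitely counted as early foetal deaths goes further than the documents allow. This part of the reply stands. It does not close the matter, because 12.5.2 also places induced abortion inside foetal death and the SAP is silent. It does nothing for the gap, which remains under the natural reading too.

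The reply can add that the stakes are modest. Early foetal death is not among the key endpoints in Protocol Section 1, and it gets summary statistics only. Foetal deaths are adjudicated for cause (Protocol 12.7.3, Table 12-2), and the causes of induced abortions are always reported as SAEs, so case-level review stays possible. This also stands. But adjudication there yields a cause of death, and SAP 5.4.3 ties only major abnormalities to the committee's classification. A late-delivered early death would show as not live born, yet the live-born endpoint in Protocol 4.4 and SAP 1.1.2.2 is missing from the analysis lists in 17.4.2.3 and 5.4.3.

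A reader might also build a count of misclassified cases from the assumption in Protocol Section 17 that at most 10% of women deliver before week 16. That figure is a ceiling for a different cut-off, and no share of terminations is given, so no count follows. Nor do the documents show that elective decisions would differ by arm. The open-label design, and approval in pregnancy for insulin detemir but not insulin degludec, make that possible and no more.

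**Conclusion.** The point holds as a contradiction between the endpoint and the protocol's own glossary. The gap is certain on the text: a death before 20 completed weeks with delivery at or after 20 is in neither early foetal death nor perinatal mortality. The counting of induced terminations is a possible outcome of the wording, not an established one.

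The number of pregnancies affected is unknown and may be zero, and cases in the gap are likely to be rare. On the assumption of about 94 women per arm, each reclassified pregnancy shifts an arm's rate by about 1.1 percentage points. The endpoint is supportive and descriptive, so no test or primary conclusion is at risk. The correction should still be made, because following the text can give a wrong safety table and the remedy is cheap.

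**What to change.** In Protocol 4.4 and 17.4.2.3 and SAP 1.1.2.2 and 5.4.3:

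1. Replace the delivery-based bracket with the glossary definition: the foetus died before 20 completed gestational weeks, regardless of when delivery took place.
2. State that induced termination of a living foetus is counted in neither early foetal death nor perinatal mortality.
3. Tabulate induced terminations by arm as an outcome category of their own.
4. State that ectopic pregnancy remains an early foetal death, as in the glossary.
5. Reconcile the opening paragraph of Protocol 12.5.2 with its later paragraphs on foetal or neonatal death and on induced abortions.

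The cost is wording and one table row. Induced abortion and gestational age are already listed for recording in 8.4.2. The drawback is that date of foetal death is not a listed eCRF item there, so the SAE onset date or the date of diagnosis may have to stand in for it. The SAP should name which one.
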